9.3. Protocol Deviations

A protocol deviation is any noncompliance with the clinical trial protocol, International Conference on Harmonisation Good Clinical Practice (ICH GCP), or Manual of Procedures (MOP) requirements. The noncompliance may be either on the part of the participant, the investigator, or the study site staff. As a result of deviations, corrective actions are to be developed by the site and implemented promptly.

These practices are consistent with ICH GCP:

- 4.5 Compliance with Protocol, sections 4.5.1, 4.5.2, and 4.5.3
- 5.1 Quality Assurance and Quality Control, section 5.1.1
- 5.20 Noncompliance, sections 5.20.1, and 5.20.2.

Anticipated deviations in the conduct of the protocol will not be reported to the IRB unless they occur at a rate greater than anticipated by the study team, in accordance with findings from previous trials as outlined in the IB. If the rate of these events exceeds the rate expected by the study team, the events will be classified and reported as though they are unanticipated problems. Deaths related to the natural history of COVID-19 will be reported at the time of continuing review.

It is the responsibility of the site investigator to use continuous vigilance to identify and report unanticipated deviations within 7 working days of identification of the protocol deviation, or within 7 working days of the scheduled protocol-required activity.

9.4. Publication and Data Sharing Policy

The PI and study team share de-identified or identified data generated in this study with all collaborators and will have access to all data collected from all sites.

This study will be conducted in accordance with the following publication and data sharing policies and regulations:

This study will comply with the Clinical Trials Registration and Results Information Submission rule. As such, this trial will be registered at ClinicalTrials.gov, and results information from this trial will be submitted to ClinicalTrials.gov. In addition, every attempt will be made to publish results in peer-reviewed journals. Data from this study may be requested from other researchers 2 years after the completion of the primary endpoint by contacting the study Sponsor.

At the conclusion of the study, the Sponsor will support the writing and publication of scientific reports, journal papers and oral presentations by the study principal investigator and others making scientific contribution to the research effort. Any reports, papers, and/or presentations must be reviewed and approved by prior to submitting for publication. All reports generated by this study will be in accordance with the ethical standards of the responsible committee on human experimentation and the Helsinki Declaration of 1975, as revised in 1983.

All publications relating to the study will comply with the guidelines set forth by the Uniform Requirements for Manuscripts Submitted to Biomedical Journals drawn up by the International Committee of Medical Journal Editors.

9.5. Conflict of Interest Policy

The independence of this study from any actual or perceived influence is critical. Therefore, any actual conflict of interest of persons who have a role in the design, conduct, analysis, publication, or any aspect of this trial will be disclosed and managed. Furthermore, persons who have a perceived conflict of interest will be required to have such conflicts managed in a way that is appropriate to their participation in the design and conduct of this trial.

10. STATISTICAL ANALYSIS

10.1. Sample size

In the phase III trial, the patients will be randomized at 1: 1 ratio into CD24Fc or placebo arms. It was assumed that the time to improvement the clinical status of the patients obeyed the exponential distribution, and the improvement hazard ratio (HR) was 1.54. The median time to improvement in the control group is presumed 11 days, and the median time to improvement in the treatment group is projected as 7.14 days. An interim analysis for efficacy will be performed when 70% of the required events are reached. The O'Brien-Fleming type consumption function of the Lan-DeMets algorithm is used to control the overall class I error rate $\alpha = 0.025$ (one-sided), at least 80% of the degree of confidence. At least 208 events are required to achieve 80% power. Assuming 28 days of patient follow up, the estimated number of 208 events will be reached for the final analysis approximately 28 days after the last subject is enrolled. Assuming 78% recovery rate, 270 participants will be enrolled in this trial.

The sample size was calculated on SAS 9.4 PROC SEQDESIGN.

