- 6) Women of childbearing potential, under the age of 54 years, who use adequate contraception and who agree to use adequate contraception for the duration of the study.

Exclusion criteria:

- 1) Patients who are pregnant, breastfeeding, or have a positive pregnancy test result before enrollment.
- 2) Patients who previously enrolled in CD24Fc clinical trial.
- 3) Intubation for invasive mechanical ventilation is over 7 days.
- 4) Documented acute renal or hepatic failure;
- 5) The investigator believes that participating in the trial is not in the best interests of the patient, or the investigator considers unsuitable for enrollment (such as unpredictable risks or subject compliance issues).

Treatment Description:

The Phase III study will be a randomized double-blind placebo controlled study in 270 subjects. Patients will be randomized 1:1 to receive one of the following treatments:

Arm A: CD24Fc, 480mg, diluted to 100ml with normal saline, IV infusion in 60 minutes.

Arm B: placebo, normal saline 100ml, IV infusion in 60 minutes.

The best available treatment and supportive care will be given to all subjects according to local institutional guideline. Those who uses immune modulators such as IL-6/IL-6R antagonists or experimental antiviral drugs such as remdesivir or convalescent plasma are allowed to participate the trial.

Accrual Objective:

The study will enroll 270 patients, or 135 per arm.

Accrual Period:

The estimated accrual period is 5 months.

Study Duration:

Patients will be followed for 28 days.

Interim Analysis:

The Phase III study will include one interim analysis:

Stopping Guidelines:

The interim analysis will be at the time when the required number of events is at 70% for the purpose of sample size re-estimation only.

Monitoring of the safety endpoint will be conducted by the CRO in a blinded fashion. The CRO will collect the data and share this with the DSMB at two safety reviews, respectively when 50% or 75% of enrolled patients reached D15. DSMB may call a meeting with the DSMB at other times if needed. DSMB may recommend early termination if it

find significantly higher SAE in the CD24Fc arm after considering the clinical benefit of the treatment. The final decision will be made by the sponsor.

Figure 1: Diagram of the study.

[figure not shown]

Table 1: Inclusion and Exclusion Criteria and NIAID 8-Point Scale for COVID-19.

Inclusion Criteria	Exclusion Criteria	NIAID 8-point scale for COVID-19

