10.5. Interim Analysis and Stopping Rules

This study will establish an independent Data and Safety Monitoring Board (DSMB) for interim analysis. The composition, task responsibilities and implementation details of DSMB will be specified in the DSMB charter.

Two blinded safety reviews will be performed, respectively, when 50% and 75% of the planned enrollment has occurred with follow-up time reaching D15 and mortality data are available.

The study will also include an interim analysis at 70% of the required 146 events. The final analysis will be carried out after all 270 subjects have been randomized, dosed and completed the study.

In the interim analysis, the DSMB will re-estimate the sample size to determine whether it supports increasing the number of clinical improvement event targets. Chen's method will be used to re-estimate the sample size (37).

Safety reviews and stopping rules

The study have two blinded safety reviews respectively, when 50% and 75% of the planned enrollment has occurred with follow-up time reaching Day 15 and SAE data are available. DSMB will be provided with list of SAE including mortality and may unblind the data at its discretion to evaluate the balance of SAE in the two study arms.

Stopping rules

If the DSMB found that SAE is significantly higher in the CD24Fc arm, it may recommend termination of the trial after review of potential benefit of the study drug by unblinding all study subjects. Sponsor will make final decision based on the recommendation of DSMB.

Sample Size Re-Estimation

The interim analysis for the primary endpoint only will be performed after reaching 146 events (70% of information). A sample size reassessment of efficacy will be performed.

There sample size re-estimation 146 events will be based on preliminary data that are not 100% source-verified. The method will be based on Chen et al as stated in the protocol. If the conditional power is < 50% or >85%, the trial will continue without a sample size increase; whereas if the conditional power is between 50% to 85%, the sample size will be re-calculated to

have 85%. To maintain trial integrity, the DSMB will pick a sample size in a nearest interval with 5 patients. For example, if the re-estimated sample size is 287, the DSMB could pick any number in the interval of 285 to 289. Also, the maximum increased sample size will not be more than 70 patients above what is needed to observe 208 events.

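### Section 10.1 still plans an efficacy interim with alpha spending, while the synopsis and 10.5 describe a re-estimation look with a final two-sided cutoff of 0.05; 208 events also do not match the stated 80% power

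*Combined protocol and SAP*

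**What the plan says.** Three places in the current protocol describe the look at 70% of events.

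- **Section 10.1 (Sample size):** "An interim analysis for efficacy will be performed when 70% of the required events are reached". It adds that an O'Brien-Fleming type "consumption function of the Lan-DeMets algorithm is used to control the overall class I error rate", set at 0.025 one-sided. It gives no interim boundary and no final cutoff. It then says "At least 208 events are required to achieve 80% power" and "The sample size was calculated on SAS 9.4 PROC SEQDESIGN".
- **Synopsis (Interim Analysis / Stopping Guidelines):** the look is "for the purpose of sample size re-estimation only".
- **Section 10.5 (Interim Analysis and Stopping Rules):** "the DSMB will re-estimate the sample size to determine whether it supports increasing" the event target. The look comes at 146 events, and "if the conditional power is between 50% to 85%, the sample size will be re-calculated" to reach 85%. No efficacy boundary is given. The final cutoff is two-sided 0.05, which the section attributes to the Lan-DeMets O'Brien-Fleming function. The final analysis is triggered by 270 patients completing 28 days.

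Section 11.2 (Study Discontinuation and Closure) also lists demonstrated efficacy, and a finding that the primary endpoint has been met, among circumstances that may warrant termination.

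**The concern.** One look at the primary endpoint cannot both test efficacy under a spending function and serve re-estimation alone. Someone programming from 10.1 would test at 146 events and lower the final level. Someone programming from 10.5 would do neither. A final p-value between about 0.0455 and 0.05 would then be a success under one section and a failure under the other.

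The 208-event target stands in the same paragraph as the efficacy interim and is presented as the output of a sequential-design procedure. If the interim no longer tests efficacy, the basis of 208 has to be stated again, and the stated 80% power can be checked directly.

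**Working it through.** **Inputs from 10.1:** hazard ratio (HR) 1.54 (medians 11 and 7.14 days; 11/7.14 = 1.541), 1:1 allocation, overall alpha 0.025 one-sided, 208 events, 80% power, 78% recovery, 270 patients. **From 10.5:** look at 146 events, increase only if conditional power is 50% to 85%, target 85%, at most 70 extra patients, final cutoff two-sided 0.05.

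**1. The plan's own counts.** 0.70 × 208 = 145.6, so 146 reproduces. 208/0.78 = 267, close to 270.

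**2. What 10.1 implies for the cutoffs.** Information fraction t = 146/208 = 0.702. The O'Brien-Fleming type spending function is α(t) = 2[1 − Φ(2.2414/√t)].

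- Interim: α(0.702) = 0.00747 one-sided, so z = 2.434, two-sided 0.0149.
- Final: solving P(Z₁ > 2.434 or Z₂ > c) = 0.025 with correlation √t gives c = 2.000, two-sided **0.0455**.

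With no efficacy look, all of the alpha remains at t = 1 and the cutoff is two-sided **0.05** (z = 1.96).

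In observed-effect terms, using exp(2z/√events), the smallest significant HR at 208 events is exp(2 × 2.000/√208) = 1.320 under the first rule and exp(2 × 1.96/√208) = 1.312 under the second.

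**3. The two rules mixed.** P(Z₁ > 2.434 or Z₂ > 1.96) = **0.0271** one-sided, ignoring re-estimation.

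**4. Power of 208 events (Schoenfeld).** ln(1.54) = 0.4318.

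- One final test: Φ(0.4318 × √208/2 − 1.96) = Φ(3.114 − 1.960) = **0.876**.
- With the efficacy interim: 0.871.
- Events for 80%: 4(1.960 + 0.842)²/0.4318² = 168.4, so **169** with one final test; **171** with the interim.
- If 0.025 were taken as two-sided, 80% power would need 204 events (Schoenfeld) or 211 (Freedman), which bracket 208. Section 10.1 labels 0.025 as one-sided, so this is only a possible origin of the figure.

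**5. Re-estimation alone, final test at z = 1.96.** Type I error was obtained by integrating over the interim Z. When conditional power was in the 50% to 85% zone, events were raised from 208 to the smallest number giving 85%, up to a cap. The cap of 55 extra events is an assumption (70 × 0.78 = 54.6).

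| Conditional power computed under | One-sided error |
|---|---|
| Observed trend | 0.0240 |
| Design HR 1.54 | 0.0253 |

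Section 10.5 does not say which basis applies. It refers to a cited method that was not available for this check.

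**The case against.** The strongest reply is that 10.5 is the dedicated interim section, it agrees with the synopsis, and 10.1 gives no boundary anyone could program. The surviving efficacy sentence could be called leftover text. Much of that stands, and it is why the point is minor. It does not remove the conflict: 10.1 is current text and also carries the alpha and power statements.

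A reader might infer more than the documents support:

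- **That the trial's type I error is inflated to 0.027.** This needs an efficacy boundary at the look together with 0.05 at the end. No section prescribes that pair.
- **That 0.05 is numerically wrong in 10.5.** It is not, if the look spends nothing: the spending function then returns the full alpha at the end. The attribution is redundant and misleading, because it suggests that alpha was spent earlier.
- **That 10.5 itself says the look is for re-estimation only.** That restriction is explicit in the synopsis. Section 10.5 reaches it by describing nothing else.
- **That the leftover interim explains 208 events.** It moves the 80% requirement only from 169 to 171.
- **That observed-trend conditional power is the planned rule.** The text does not state the basis.

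**Conclusion.** The inconsistency is real but minor. The synopsis and 10.5 agree on the working rule: re-estimation at 146 events and one final test at two-sided 0.05. Section 10.1 was not aligned with them. The competing final cutoffs are 0.0455 and 0.05, a difference of about 0.008 in the smallest significant HR. The 0.0455 assumes 208 events at the final analysis.

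Separately, 208 events and 80% power do not fit together under the stated inputs. Power is about 87.6%, so the mismatch is on the conservative side and does not call for more patients.

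Whether the re-estimation rule alone keeps one-sided error at or below 0.025 depends on the unstated conditional-power basis: 0.0240 or 0.0253, under the assumed cap of 55 events.

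**What to change.** 1. **10.1:** replace the efficacy-interim and spending sentences with: *One look at 146 of 208 events (70%) is for sample-size re-estimation only; it makes no efficacy decision and spends no alpha. The primary endpoint is tested once, at the final analysis, at two-sided 0.05.*
2. **10.5:** delete the clause that attributes the 0.05 cutoff to the O'Brien-Fleming function.
3. **11.2:** reconcile the items on stopping for efficacy or for a met primary endpoint with a look that makes no efficacy decision.
4. **10.1:** state the power of 208 events as about 87.6% under the given inputs, or state the other assumptions behind 208. Enrolment stays as planned.
5. **10.5:** state which conditional-power basis the cited method uses, and confirm that one-sided error stays at or below 0.025. Change the final-analysis trigger to *270 or the re-estimated number*.

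If an efficacy look is wanted after all, say so in 10.1, 10.5 and the synopsis, and compute the final boundary from the spending function at the realised number of events. A fixed figure would not do, because the final analysis is triggered by patients: with 146 events at the look, the final two-sided cutoff is 0.0437 at 190 events, 0.0455 at 208 and 0.0463 at 220 (both boundaries recomputed each time).

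The cost is protocol wording, one restated power calculation and one type I error check. No patients or data are affected. It is best done before the 146-event look.

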For the primary endpoint, during the observation period, an improvement from NIAID scale 2, 3 or 4 to scale 5 or above, if sustained without a drop below 5, is considered as an event. The days from the randomization to the first time point of such improvement will be defined as time of improvement. Additional follow-up can be used to determine clinical improvement events.

Subjects who do not withdraw or do not experience improvement will be censored on the actual date of the D29 visit.

Subjects without improvement but lost to follow-up will be censored on the last date of follow-up.

Subjects with death within 28 days will be censored on D29.

Sensitivity analysis:

(1) Imbalances in age, baseline score, use of antiviral drugs such as remdesivir, or IL-6/IL-6R antagonist, or related factors that may affect the results will be investigated with sensitivity analyses and these factors will be evaluated separately in the Cox-Model to assess their potential impact on the primary efficacy endpoint.

(2) Use only data from planned visits to analyze time to improvement in the main analysis.

(3) The days from randomization to the first clinical improvement will be analyzed.

Since there are no available best supportive case (BSC) for this disease, controlling BSC use between two arms is difficult, and consequently there may be imbalance for some particular BSCs between two arms. To evaluate whether there may be some potential bias caused by such imbalance, we will evaluate the percentage of the largest and second largest BSC used in the trial if the difference of such BSC between two arms are significant. Further analyses will be performed to study whether the efficacy results are indeed caused by such differential BSC use between two arms.

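### Section 10.1 calls 208 events the requirement for 80% power, but its own inputs give about 87%; its 78% recovery rate does not match its medians, and it keeps an efficacy interim that the synopsis and 10.5 no longer have

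*Combined protocol and SAP*

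**What the plan says.** Section 10.1 assumes exponential times to improvement, an HR of 1.54, a control median of 11 days, and that "the median time to improvement in the treatment group is projected as 7.14 days". The error rate is one-sided 0.025. It then states "At least 208 events are required to achieve 80% power" and "Assuming 78% recovery rate, 270 participants will be enrolled in this trial". On the interim it says: "An interim analysis for efficacy will be performed when 70% of the required events are reached", with Lan-DeMets O'Brien-Fleming spending.

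Other current sections differ on the interim. The synopsis (Stopping Guidelines) says it is "for the purpose of sample size re-estimation only". Section 10.5 describes re-estimation and gives no efficacy boundary. It sets the final cutoff at two-sided 0.05 but attributes that value to the O'Brien-Fleming spending function. Section 10.5 also gives two versions of the timing: "The study will also include an interim analysis at 70% of the required 146 events", and later "after reaching 146 events (70% of information".

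Section 10.4.1 adds, for the primary endpoint: "Subjects with death within 28 days will be censored on D29".

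**The concern.** The 80% is the plan's only statement of power for the primary endpoint, and it does not follow from the inputs printed beside it. The same paragraph uses two recovery rates that cannot both come from its exponential model, and whether true power lies above or below 80% depends on which departure from the model produces the 78%. The re-estimation rule in 10.5 is anchored on 208 events, so that figure should be traceable.

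The interim wording is a separate matter. A reader of 10.1 would expect alpha to be spent at 70% of events, and a reader of 10.5 would expect none to be spent. The two readings lead to different final cutoffs.

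**Working it through.** **Inputs (all from 10.1).** HR 1.54 (check: 11/7.14 = 1.541); 1:1 allocation; one-sided 0.025 (z = 1.960); 80% power (z = 0.842); 208 events; 78% recovery; 270 patients; 28 days of follow-up.

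**1. What can be reproduced.** 208/0.78 = 266.7, consistent with 270. 0.70 × 208 = 145.6, which gives the 146 in 10.5. The 208 itself cannot be reproduced:
- Schoenfeld: 4 × (1.960 + 0.842)² / (ln 1.54)² = 168.4 events.
- With one O'Brien-Fleming look at 70%: 170.9 events.
- Freedman: (1.960 + 0.842)² × (2.54/0.54)² = 173.7 events.

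Rounded up, these are 169, 171 and 174, so 208 is 34 to 39 events too many.

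**2. Power at 208 events.**
- Schoenfeld: Φ(√208/2 × ln 1.54 − 1.960) = Φ(3.114 − 1.960) = 87.6%.
- With the look: 87.1%.
- Freedman: Φ(√208 × 0.54/2.54 − 1.960) = Φ(3.066 − 1.960) = 86.6%.

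The HR at which 208 events give 80% is exp(2 × 2.802/√208) = 1.475.

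**3. A possible source of 208.** If 0.025 is entered as a two-sided level, Schoenfeld gives 204 events, 206 with the look, and Freedman gives 211. Power at 208 is then 80.8% (80.4% with the look). This would contradict both the one-sided 0.025 in 10.1 and the two-sided 0.05 in 10.5. The documents do not confirm it.

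**4. Recovery by day 28 under the stated medians.**
- Control: 1 − 2^(−28/11) = 82.9%.
- Treatment: 1 − 2^(−28/7.14) = 93.4%.
- Mean: 88.1%, and 0.881 × 270 ≈ 238 events.
- At 78%: 0.78 × 270 = 210.6 events.

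**5. Power with 270 patients under different explanations of the gap** (simulated log-rank test, 135 per arm, one-sided 0.025):

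| Assumption | Events | Power |
|---|---|---|
| Stated medians, no shortfall | 238 | about 92% |
| Independent loss to follow-up giving 78% | 211 | about 88% |
| Slower recovery, same HR (medians about 15.7 and 10.2 days) | 211 | about 88% |
| 5% never improve, equal in both arms | 226 | 81 to 82% |
| 11.5% never improve, equal in both arms | 211 | about 68% |

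The 11.5% is 1 − 0.78/0.881, the share that turns 88.1% into 78% at the stated rates. The shares, and their equality across arms, are assumptions that the documents do not give. Under the censoring rule in 10.4.1, patients who die stay in the risk set to D29, as they do in the last two rows.

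**6. Final cutoff.** Lan-DeMets O'Brien-Fleming spending at 70% information uses one-sided 0.0074 at the look (z = 2.438) and leaves z = 2.000 at the end, a two-sided 0.0455. A final 0.05 therefore fits an interim with no efficacy test and does not fit the spending function to which 10.5 attributes it.

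**7. Re-estimation rule in 10.5.** This is a numerical integration under the null: look at 146 events, increase only when conditional power is 50 to 85%, target 85%. The 70-patient cap is taken as a maximum of 263 to 278 events (208 + 0.78 × 70 = 262.6; 208 + 70 = 278). One-sided error is about 2.4% if conditional power uses the observed trend and about 2.53% if it uses the design HR.

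**The case against.** The strongest reply is that the error is on the safe side. Section 10.1 words both the events and the power as minimums, and under a constant HR of 1.54 the trial has more power than claimed. The final analysis in 10.5 waits until 270 patients have completed follow-up, which on the stated medians means about 238 events and about 92% power. This stands under the stated model. It does not make the 80% correct, and it does not explain the 78%.

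A reader might infer from the 78% that the trial is underpowered. The documents do not support that. Patients who never improve do not by themselves bring power below 80%: at an equal 5% share it is still 81 to 82%. If the drug also reduces that share so that the HR of 1.54 holds over the whole curve (assumed 14.4% on control, 5.1% on treatment), pooled recovery is 78% and simulated power is 87.4%. The loss comes from an equal share in both arms, which abandons the constant HR of 10.1.

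A reader might also infer that the 0.05 test is invalid because an efficacy look spends alpha. The synopsis and 10.5 together point to re-estimation only, and then 0.05 is not put at risk by the leftover text in 10.1. Section 11.2 does still list shown efficacy and a met primary endpoint among the grounds for ending the trial, which needs reconciling.

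The conditional-power point is small. Section 10.5 names its method by reference, which may already fix the effect to be used, and the worse case is about 0.03 percentage points above 2.5%.

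**Conclusion.** The concern holds as a mismatch in the stated justification; it does not show that the trial is too small. On the inputs of 10.1, 208 events give about 87% power (86.6 to 87.6% by method), and 80% would need about 168 to 174. This rests on a constant HR of 1.54 at one-sided 0.025.

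The medians and the 78% are inconsistent by about 10 percentage points, or 27 events in 270 (238 − 211). What that does to power cannot be settled from the documents: it ranges from about 88% down to about 68% over the explanations tried that reproduce 78%, and the low figure depends on an assumed equal never-improving share.

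The efficacy interim in 10.1 conflicts with the synopsis and 10.5, and the attribution of 0.05 to the spending function is wrong for a look at 70%. The first of the two timing sentences in 10.5, read literally, means 0.70 × 146 = 102 events; this is a slip that the same section later corrects.

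**What to change.** Keep 270 patients, 208 events and the two-sided 0.05 test.

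- **10.1, power.** Check the alpha entered in PROC SEQDESIGN first. Then write: 208 events give about 87% power for a constant HR of 1.54 (80% for an HR of about 1.475) at one-sided 0.025.
- **10.1, recovery rate.** Say whether the 78% reflects loss to follow-up, slower recovery at the same HR, or patients who never improve (and if so, whether equally by arm). Give the power under that assumption.
- **10.1 and 10.5, interim.** Delete the efficacy-interim and spending-function wording from 10.1 and the spending-function attribution of the final cutoff in 10.5. Reconcile the efficacy grounds for termination in 11.2 with a re-estimation-only interim. If an efficacy look is kept instead, state its boundary in 10.5 and use 0.0455 as the final cutoff.
- **Minor, 10.5.** Write 146 events (70% of the required 208), and state the effect under which conditional power is computed.

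The cost is wording plus one rerun of the power calculation once the 78% is explained.
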